We employed the G* Power version 3.1.9.7 software program to calculate the sample size based on the specified parameters.: a total sample size of approximately ..., an effect size of 0.5, α error probability of 0.05, Power (1- β error probability) of 0.95, two groups, three measurements, and a correlation among repeated measures of 0.5. The program recommended a minimum sample size of 140 nurses. However, the researchers decided to recruit 150 nurses for both the control group and the study group.

[figure not shown]
To be eligible for the study, nurses had to be.....

As shown in figure (1), each randomly selected nurses were screened to identify the student who met the predetermined inclusion criteria. Three students refused to participate and were excluded due to lack of inclusion criteria. A comprehensive list of the rest, containing the names and relevant data of all students was compiled. The participants were assigned to either the control or study group using a computer-generated randomization list (....each). This random assignment ensured fairness and minimized bias.nurses were withdrawn from either the control or intervention group

Table 1: Stratified random sample using proportion allocation technique.

Academic Level	Strata according to the department	The Expected population size of each stratum	Proportionate sample size in each stratum
1			
2			
3			
4			

Total	Size of the entire population=	Total sample size = 150
--------------	---------------------------------------	--

Intervention (n=62)
Completed post-intervention assessment=60
Lost or dropped out in second post-test = 2

Control (n=61)
Completed post-intervention assessment=60
Lost or dropped out in second post-test = 1
(Not included in the analyse)

Analyzed (n=60)

Analyzed (n=60)

CONSORT analysis of nurses' enrollment and recruitment process

Follow up

Analysis

Tools of data collection: A questionnaire sheet was used to collect data for this study and composed of five parts:

Part (1): This covers staff nurses ' demographic information such as age, department, education level, years of experience, and previous training in job crafting.

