head nurses of the departments were briefed on the upcoming research. This step was included as this may aid in the effectiveness of the intervention as they may stimulate and motivate the nurses to part-take in the intervention with motivation and enthusiasm. The pre-test forms have been given to nurses to determine their training needs regarding job crafting and job crafting behavior among Nurses. The data were gathered during morning and afternoon shifts for four days / week. The time each staff nurse needed to complete each sheet varied from 25 to 30 minutes. The learning needs of nurses were established based on pre-test results. Accordingly, the program's goals have been set out and the content developed.

Implementation phase: ((please insert in table with sessions name, objective, time, steps).

The training program designed for this study was implemented through twelve sessions, from which three theory and nine practical sessions were held in a room at the worksite. The sessions were conducted outside of working hours in the hospital. These sessions lasted 21 hours; 3 theory hours (one hour for each theoretical session); and 9 practical sessions (two hours for each practical session). Having the whole number of nurses at the same time was difficult, so the nurses were classified into five groups each group consisting of about 16 nurses. All sessions were repeated to the five main groups until 80 nurses completed the entire 21-hours instruction period.

The program includes three main parts;

the first theoretical part covers knowledge of the job crafting, job crafting theory, Job Demands–Resources model, definition work environment, combine work environment and JD- R model. Then, based on examples from structured interviews conducted before the program, examples of job crafting are provided, as well as examples of a work analysis. Success stories of past job crafting behaviors of staff nurses were shared and discussed. This was helpful to reflect on the current work performance, and then made their own individual job crafting plans.

The second practical part was included to guide the employees on how to craft their daily activities and to give them suggestions on craft-able work-related activities as 1- increasing job Resources e.g. ask feedback, ask support, ask for help from colleagues or your leaders if you need help, participate committees, look for trainings, invest in

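### The sample counts (150, 80, 8 as 10%, 62/61) do not agree, the effect size behind the minimum of 140 is undefined, and this trial's control condition is not described

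*Protocol*

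**What the plan says.** **Planned numbers.** The Protocol's Sample size section lists an effect size of 0.5, alpha 0.05, power 0.95 and "two groups, three measurements, and a correlation among repeated measures of 0.5". It then reports: "The program recommended a minimum sample size of 140 nurses". It goes on to say that "the researchers decided to recruit 150 nurses for both the control group and the study group". Table 1 settles that 150 is the overall figure: "Total sample size = 150". The number per arm was never filled in; allocation was made "using a computer-generated randomization list (....each", with dots where the number should stand.

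**Flow text.** Beside the missing figure, the text shows "Intervention (n=62" for the program arm and 61 for control, with 2 and 1 lost at the second post-test and 60 analysed in each arm.

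**Pilot study.** Eight nurses took part, described as 10% of the research sample.

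**Implementation phase.** Because all nurses could not attend together, "the nurses were classified into five groups each group consisting of about 16 nurses". The section ends the count with: "All sessions were repeated to the five main groups until 80 nurses completed the entire 21-hours instruction period". The program has twelve sessions, three of theory and nine practical.

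**Control condition.** From the aim of the study to the Statistical design section, nothing says what control nurses receive. A control description appears only in section 3.6. It closes a Theoretical Framework and Methods text (sections 3.1 to 3.6) that follows the reference list without any label. There, controls received the content of the first two sessions of a four-session workshop.

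**The concern.** A randomised comparison needs a fixed number per arm and a defined comparator. Here the number trained, the pilot percentage and the stated total cannot all be right, so the size of the program arm cannot be established from the document.

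The sample-size statement cannot be checked either, because neither the metric of the 0.5 nor the effect being tested is named, and the number shown as analysed is below the protocol's own minimum.

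The comparator matters most. A reader looking for the control condition will find section 3.6 and may take it as this trial's. A control arm given part of the program and one given nothing define different contrasts, so the meaning of any between-arm difference depends on a statement that the trial's own text does not make.

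**Working it through.** **1. Head-counts.** Inputs: 150 (Sample size, Table 1); 62, 61, 60 and 60 (flow text); 8 as 10% (Pilot study); five groups of about 16, and 80 completing (Implementation phase).

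- Trained: 5 × 16 = 80, which matches the stated 80.
- Equal arms: 150 / 2 = 75, and 80 − 75 = 5 too many. The equal split is inferred from the unfilled number given for each group.
- Pilot: 8 / 0.10 = 80. Against 150, 10% is 15, and 8 / 150 = 5.3%.
- If 80 is one of two equal arms, the total is 2 × 80 = 160, which is 10 above 150.
- If 80 is the whole sample, training all 80 leaves 80 − 80 = 0 controls, and Table 1 is contradicted.
- Flow: 80 − 62 = 18 and 62 + 61 = 123. The stage of these counts is not shown, so the 18 is a gap to explain and not a proven contradiction.

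**2. The minimum of 140.** Assumed method: repeated-measures ANOVA with k = 2 groups, m = 3 measurements, correlation ρ = 0.5 and alpha 0.05, with power from the noncentral F distribution.

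- Between-group effect: λ = N f² m / (1 + (m − 1)ρ), with 1 and N − 2 degrees of freedom.
- Group-by-time interaction (G*Power default): λ = N f² m / (1 − ρ), with 2 and 2(N − 2) degrees of freedom.

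Reading 0.5 as d gives f = 0.25 for two equal groups. For the between-group effect at N = 140, λ = 140 × 0.0625 × 3 / 2 = 13.125 and power is 0.949. The first even N that reaches 0.95 is 142. This roughly reproduces 140.

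| Reading of 0.5 | Effect | N for 0.95 | Power at 120 |
|---|---|---|---|
| d (f = 0.25) | between groups | 142 | 0.914 |
| d (f = 0.25) | interaction | 44 | above 0.999 |
| f = 0.5 | between groups | 38 | above 0.999 |
| f = 0.5 | interaction | 14 | above 0.999 |

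Other variants do not reproduce 140 either. With f = 0.5, the alternative effect-size options for the interaction need 64 or 36 and a one-way comparison needs 54, all with power above 0.99 at 120. With f = 0.25, the same variants need 250, 128 and 210, with power at 120 of 0.68, 0.94 and 0.78.

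**3. The shortfall.** Analysed: 60 + 60 = 120. Then 140 − 120 = 20, or 20 / 140 = 14.3%. On the reading that fits, λ at 120 is 120 × 0.0625 × 3 / 2 = 11.25. Power is 0.914 against 0.949 at 140 and 0.961 at 150. The d detectable with 0.95 power is 0.54 at 120 and 0.50 at 140.

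**4. Comparator.** The two sets of Methods side by side:

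| Item | This trial's own text | Text after the references |
|---|---|---|
| Setting | Zagazig University Emergency Hospital | a health insurance hospital in Port Said |
| Sample | 150 in total | 94 (47 per group) |
| Program | twelve sessions, 21 hours (3 × 1 + 9 × 2) | 2-day, four-session workshop, 3 weeks of practice, reflection session |
| Outcomes | job crafting, meaningfulness, change attitude, task and adaptive performance | harmonious work passion and career commitment |
| Registration | identifier left blank | its own identifier |
| Control condition | not stated | sessions one and two of the workshop |

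The outcomes on the right are those of the 2023 trial that the Introduction summarises. The first two sessions of a four-session workshop have no stated counterpart in a twelve-session program.

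**The case against.** **The counts may differ only by stage.** Completing the instruction and providing a post-test are different points, the earlier flow boxes are not visible, and a sentence in the Sample size section mentions withdrawals without a number. This stands for 80 against 62. It does not remove the 80 against 75, apart from the assumption of equal arms, and it does not touch the pilot percentage.

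**The flow figures are no firmer than the 80.** The surrounding text speaks of students and academic level, apparently carried over from another study. This stands: 62, 61, 60 and 60 need checking as much as 80 does, and the count of 120 depends on them.

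**The loss of power is conditional.** The 0.914 requires both that 0.5 is d and that the between-group effect is tested, and even then the exact answer is 142. The hypotheses speak of increases, which points towards a group-by-time test, and its power at 120 is above 0.999 with f = 0.25 under the default formula. The Statistical design section names only a paired t-test and a Pearson correlation, so 0.914 is not the power of any test the protocol states. This stands. A reader might infer that the trial lacks its planned 0.95 power, but the document does not support that without conditions.

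**Control nurses may seem to have been trained.** A reader might infer this from 80 exceeding 62 or 75. No passage indicates it, and an uncorrected draft figure or earlier losses would explain the gap equally well.

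No comparable defence exists for the missing control condition. It is a core element of a protocol and is not commonly left to a statistical analysis plan.

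**Conclusion.** The point holds in three parts of unequal weight.

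- **Comparator (most serious).** The trial's own text does not define what the control arm receives, and the only description available belongs to a different trial with a different program.
- **Counts.** A total of 150 does not fit 80 trained nurses in equal arms (5 too many) or a pilot of 8 called 10% (15 would be needed). The 5 rests on equal allocation; the pilot mismatch rests on no assumption beyond Table 1's total. The gap of 18 against the flow text is unexplained but not a proven contradiction.
- **Sample size (minor).** The 120 shown as analysed are 20 below the stated minimum, and the 0.5 has neither a metric nor a tested effect. The cost is about 3.5 points of power (0.949 at 140 to 0.914 at 120) if 0.5 is d for the between-group effect. It is negligible if 0.5 is f, or if the interaction is tested at f = 0.25 under the default formula.

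The first two parts must be corrected before the document can serve as a record of the design.

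**What to change.** - Check 150, 80, 8 and 62/61 against the recruitment, randomisation and attendance records. State one total and one number per arm, fill the blank, and label the stage of every count. Correct the pilot percentage or its base.
- State from the attendance records which arm the trained nurses belonged to, so that the question does not stay open.
- Say whether 0.5 is d or f and which effect it refers to. Restate power for the number analysed, on that condition: about 0.91 at 120 if it is d for the between-group effect.
- Remove the Theoretical Framework and Methods text after the references (sections 3.1 to 3.6), or label it as the cited earlier study.
- State in the main text what this trial's own control arm received up to the three-month follow-up.

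The cost is a records check and text edits. No further participants are needed and the design does not change. The stated power may become slightly less favourable.

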To investigate the effectiveness of job crafting intervention program on job crafting behavior, work meaningfulness, change attitude, adaptive and task performance among nurses at Zagazig university hospitals.

Research hypothesis:

1. After program intervention, nurses will demonstrate an increase in job crafting behavior (increasing job Resources, increasing challenging job demands, and decreasing hindering job demands).
2. Nurses participating in the intervention program will report higher levels of work meaningfulness.
3. The experimental group will demonstrate an increase in positive work attitude and decrease in negative work attitude

4. The experimental group will experience a higher adaptive performance and perform higher levels of task performance.
5. An increase in job crafting behavior is related to and predicts work meaningfulness, change attitude, adaptive and task performance among nurses

Subjects and Methods:

Research design:

The study described in ClinicalTrials.gov with the identifier NCT.....utilized a randomized control trials research design.

Administrative & Ethical Steps:

We obtained official written authorization from the Zagazig university hospitals in order to carry out our research, following the approval of ethical considerations. Formal consent and authorization for the study were also acquired from the Research Ethics Committee within the Faculty of Nursing at Zagazig University, Egypt (IRB:). Patients were duly informed about the study's objectives, and we obtained their informed written consent. They were informed of their right to decline participation, with the assurance that their decision would not impact their care. Moreover, patients were assured that they had the option to withdraw from the study at any point, even after initiation, with the assurance of maintaining their privacy and confidentiality.

Study setting :

This study was conducted at the Zagazig University Emergency Hospital, which provides a wide spectrum of health services at El Sharkia Governorate in Egypt. This hospital receives emergency cases and injuries 3 days/week from Zagazig City and other near areas, giving care for about 7.5 million people, according to the hospital most recent statistical data. The hospital is occupied with (185) beds.

Subjects:

Include staff nurses working in different departments of Zagazig University Emergency Hospital.

Sample size :

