relationships, and clean your desk to work more efficiently. 2- increasing challenging job demands e.g. volunteer work for a committee, communication about emotional/serious issues to patients and families, offer to be responsible for making the nursing schedule in a certain month, share your head nurse in writing certain documents, and stay informed about current and recent research.3- decreasing hindering job demands e.g. simplify tasks, work more efficient, let go perfectionism, say 'no', make clear appointments, checking emails only at certain times during the day and make use of relationships. The staff nurses were then asked to conduct a personal work analysis, guided by questions in their personal action plan. They were also provided with a homework papers for a job crafting exercise. Each staff nurse reviewed his/her own job crafting plan individually (20 min); the nurses then shared their reflections as a group (30 min), discussed what job crafting would be feasible and sustainable to practice (35 min), and, finally, made a modified job crafting plan (35 min). Thereby aiming to increase awareness for the utility of job crafting in their work environment.

The third and last part

consisted of setting personal goals. These goals were aimed at the three job crafting dimensions and had to be SMART5. Complementary, the participants had to formulate actions to attain their personal goals. Each staff nurse had one week to attain his or her goal with respect to the corresponding job craft dimension of that week. The researchers used different teaching approaches to attract the attention of nurses and to inspire them to participate, such as seminars, group discussion and brainstorm. The teaching media included: power point, white blackboard and a copy of the program which covered theoretical and practical information about job crafting, Job Demands–Resources model, combine work environment and JD- R model. All data were collected using a self-report questionnaire at baseline, post-intervention, and three-month follow-up.

Evaluation phase: The impact of the educational program was measured during this phase; it was carried out immediately after the program was introduced and followed up after 3 months of implementation using the same method formats used before the program was implemented.

Administrative and ethical considerations:

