Before the research started, ethical approval was given by the Scientific Research Ethics Committee at the Faculty of Nursing-Zagazig University (NO: 056). Participants were

explained the study objective and protocol, and only those who provided informed consent were included. Voluntary participation, autonomy, and confidentiality of the information gathered were confirmed.

Statistical design:

All data were collected, tabulated, and statistically analyzed using version 20.0 of the Social Science Statistical Package (SPSS), quantitative data were expressed as mean \pm SD and range, and qualitative data were expressed as absolute frequencies (number) & relative frequencies (percentage). Paired t-test was used to compare normally distributed variables between two dependent groups. P.

Pearson correlation coefficient has been determined to determine the relationship between different variables of the sample,(+) sign indicates direct correlation and-) (sign indicates reverse correlation, even values close to 1 indicate strong correlation and values close to 0 indicate weak correlation. All testing was two-sided. P-value < 0.05 was deemed statistically significant (S), and p-value < 0.001 was considered highly statistically significant (HS), and p-value ≥ 0.05 was considered statistically insignificant (NS).

References

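### The only test of means in the Statistical design is a paired t-test, which cannot compare the two randomised arms

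*Protocol*

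**What the plan says.** - **Design.** Under Research design the study "utilized a randomized control trials research design". Under Sample size, "The participants were assigned to either the control or study group using a computer-generated randomization list".
- **Sample size.** The calculation uses an effect size of 0.5, alpha 0.05, power 0.95, "two groups, three measurements, and a correlation among repeated measures of 0.5". It gives a minimum of 140 nurses, and 150 are to be recruited.
- **Measurements.** At the end of the Implementation phase: "All data were collected using a self-report questionnaire at baseline, post-intervention, and three-month follow-up".
- **Hypotheses.** Item 4 reads "The experimental group will experience a higher adaptive performance and perform higher levels of task performance" and names no comparator. Item 2 reads "Nurses participating in the intervention program will report higher levels of work meaningfulness", again without one. Items 1 and 3 are worded as increases or decreases.
- **Analysis.** The Statistical design names descriptive statistics, then "Paired t-test was used to compare normally distributed variables between two dependent groups", then "Pearson correlation coefficient has been determined to determine the relationship between different variables of the sample". All tests are two-sided at 0.05. No independent-samples test, analysis of covariance, repeated-measures model or group-by-time term appears.

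**The concern.** The aim is the effectiveness of the program. A paired t-test in the trained nurses asks whether their scores changed, not whether the program changed them. The control arm exists to separate those two questions, and the stated analysis does not use it.

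Running the paired test in each arm does not repair this. Finding significance in one arm and not in the other is not a test of the difference between arms, and it has its own inflated error rate. A paired test also takes two of the three occasions at a time, which does not match the design behind the sample size.

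At stake is the main conclusion. As written, the trial becomes an uncontrolled before-after study and could declare the program effective when the arms do not differ. The outcomes are self-reported on the same questionnaire given three times, so some change without a program effect is plausible.

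**Working it through.** **1. What the sample size was built for.** Inputs from the Sample size section: effect 0.5, alpha 0.05, power 0.95, 2 groups, m = 3 measurements, correlation ρ = 0.5. The metric of the 0.5 is not stated. Read as Cohen's d, it corresponds to f = 0.25. For the between-groups factor of a repeated-measures ANOVA:

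λ = f² · N · m / (1 + (m − 1)ρ), with 1 and N − 2 degrees of freedom.

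At N = 140: λ = 0.0625 × 140 × 3 / 2 = 13.125, power 0.949. The smallest even N that reaches 0.95 is 142. This reproduces the stated 140 to within rounding. The other readings tried do not:

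| Calculation | Required N |
|---|---|
| Between groups, f = 0.25 | 142 |
| Between groups, f = 0.5 | 38 |
| Within or interaction, f = 0.25 | 44 |
| Within or interaction, f = 0.5 | 14 |
| Two-sample t, d = 0.5 | 210 |
| One-group paired t, standardised change 0.5 | 54 |

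So the trial appears to have been sized for a comparison between arms, which the analysis section omits.

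**2. The two readings of the stated test.** If the two dependent groups are before and after scores of the same nurses, the control arm plays no part in the test. If they are the two arms, the observations are not paired and the test is invalid. Neither reading gives a valid arm comparison.

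**3. How often the paired test would mislead.** Assume no program effect and the same true improvement of s SD in both arms. The Protocol gives neither an SD nor a time trend, so s is shown as a range.

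SD of change = √(2(1 − 0.5)) = 1 SD, so the standardised change is s. The noncentrality is s√n with n − 1 degrees of freedom. For example, with n = 75 and s = 0.3 it is 0.3 × √75 = 2.60, and the probability of p < 0.05 is 0.727.

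Probability that the paired test in the program arm is significant:

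| Shared shift s | 60 per arm | 70 per arm | 75 per arm |
|---|---|---|---|
| 0 | 5% | 5% | 5% |
| 0.1 SD | 12% | 13% | 14% |
| 0.2 SD | 33% | 38% | 40% |
| 0.3 SD | 63% | 70% | 73% |
| 0.4 SD | 86% | 91% | 93% |

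The number per arm is left blank in the Protocol. 75 is half of 150, 70 is half of 140, and 60 is the number analysed in the flow diagram. In a simulation of 20,000 trials with 70 per arm, a between-arm test of change was significant in about 5% of trials at every shift tried (0, 0.2, 0.3 and 0.5 SD).

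**4. Significant in the program arm but not in the control arm.** With the same true change in both arms the probability is p(1 − p). With 75 per arm:
- 0.2 SD: 0.401 × 0.599 = 0.24
- 0.3 SD: 0.727 × 0.273 = 0.20
- 0.4 SD: 0.928 × 0.072 = 0.07

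The ceiling is 0.25, at p = 0.5. A valid two-sided test errs in the program's favour 2.5% of the time.

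**5. Power of a valid analysis.** For a between-arm difference d = 0.5 at one time point, adjusting for baseline with ρ = 0.5 gives a residual SD of √(1 − 0.25) = 0.866. The standardised effect is 0.5 / 0.866 = 0.577. Power is 0.94 with 75 per arm, 0.92 with 70 and 0.88 with 60. Change scores without adjustment give 0.86 with 75 per arm.

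**The case against.** The strongest reply is that the control arm was plainly meant to be used. The design, the sample size and the hypotheses on the experimental group all point that way, a stray character after the paired-test sentence suggests that text may be missing, and a separate analysis plan may exist. This shows intent, but it does not change the test that the Protocol states. The Protocol is not silent here: it names a method, and that method cannot meet the aim. The repeated-measures ANOVA in section 3.3 at the end of the Protocol does not help, because that text describes the sample size of another study (Port Said, 94 nurses, other outcomes).

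Several limits do stand:
- **The drift is assumed.** With no shared shift the paired test keeps its 5% error rate, and at 0.1 SD the rate is 12% to 14%. That a shift would be read as a program effect is an inference from the plan.
- **A between-arm test removes only what both arms share.** Expectation effects in nurses who know they were trained, or encouragement by head nurses to take part in the program, would fall mainly on the program arm and remain. The statement that blinding was not feasible also belongs to the other study. For this trial, lack of blinding is inferred.
- **Power falls short of the 95% target** at a single time point. Training is also given in five groups of about 16. With five training groups in the program arm only and an assumed intraclass correlation of 0.01, 0.05 or 0.10, approximate power falls from 94% to 92%, 86% or 77% at N = 150, and from 88% to 86%, 79% or 71% at N = 120.
- **More than one between-arm model is valid.** The defect is the absence of any such comparison, not the absence of a particular model.

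**Conclusion.** The concern holds and must be fixed. The one test of means named in the Statistical design cannot compare the randomised arms on either reading of its wording, and it conflicts with a sample size that is recovered only by a between-groups calculation (power 0.949 at N = 140, with 0.5 read as d).

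Under an equal shift in both arms of 0.1 to 0.4 SD and no program effect, the paired test would be significant in 14% to 93% of trials with 75 per arm, against about 5% for a between-arm test. These rates rest on the Protocol's correlation of 0.5, equal SDs and an assumed shift. The mismatch between design and test does not depend on them.

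**What to change.** Replace the paired t-test as the effectiveness analysis. Wording along these lines would do:

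> For each outcome, all randomised nurses will be analysed in the arm to which they were assigned. A linear mixed model will include arm, time (post-intervention, three months), arm by time, and the baseline score. The adjusted difference between arms, with its 95% confidence interval, will be reported at each time. Paired comparisons within arms are descriptive only.

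Analysis of covariance at each follow-up, or a repeated-measures ANOVA judged on its group-by-time term, would also be valid. In addition:
- Word hypotheses 1 to 4 as program arm versus control arm.
- State whether the effect size of 0.5 is d or f.
- Say how the five training groups are handled in the model and in the power.

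The cost is Protocol wording and a few lines of analysis code, with no new data or participants. Within-arm p-values lose their headline role. The Field work section places the study in March to August 2023, while the document is dated 8-1-2024. If those dates are right, the change comes after data collection and should be declared as such.

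### The only comparison named is a within-arm paired t-test; the arm comparison that replaces it should adjust for the baseline score, because change-score or post-score tests would be valid but less precise

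*Protocol*

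**What the plan says.** The Implementation phase of the protocol's Field work section gives the measurement schedule: "All data were collected using a self-report questionnaire at baseline, post-intervention, and three-month follow-up". The Sample size section lists "an effect size of 0.5, α error probability of 0.05, Power (1- β error probability) of 0.95", followed by "two groups, three measurements, and a correlation among repeated measures of 0.5". It reports a minimum of 140 nurses and a decision to recruit 150; Table 1 gives 150 as the total. The flow text in the same section shows 60 analysed in each arm.

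The Statistical design section then names descriptive statistics, one comparison and a Pearson correlation. The comparison is: "Paired t-test was used to compare normally distributed variables between two dependent groups". It adds: "All testing was two-sided". It names no test between the randomised arms and no baseline covariate. The Research hypothesis section, however, makes claims about the experimental group in hypotheses 3 and 4.

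**The concern.** A paired t-test compares two occasions in the same nurses. Run in the intervention arm it says whether scores moved, not whether they moved more than in the control arm. The trial is randomised and its hypotheses concern the experimental group, so some arm comparison has to replace the paired test as the test of effectiveness.

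The shortest repair would be a two-sample t-test on the before-to-after changes (the between-arm counterpart of the paired test) or on the post scores. Either would discard precision that the collected data already hold. At a correlation of 0.5, subtracting baseline removes no more variance than ignoring it, whereas using baseline as a covariate removes a quarter. At stake is the chance of detecting a real effect of the planned size on each outcome.

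**Working it through.** **Inputs.** From the protocol: two-sided alpha 0.05, correlation 0.5, effect size 0.5, and total numbers of 120 (flow text), 140 (minimum) and 150 (Table 1). Assumed: 1:1 allocation, because the number per arm is left blank, and effect size read as a standardised mean difference d, because the metric is not named. The later methods text that describes 94 nurses at a different hospital was not used.

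**1. The plan's own 140.** I took a repeated-measures ANOVA, between-groups F-test, with m = 3 occasions, correlation ρ = 0.5 and noncentrality λ = f²·N·m/(1+(m−1)ρ).
- With f = d/2 = 0.25 and N = 140: λ = 0.0625 × 140 × 3/2 = 13.125, and power is 94.9%. Passing 95% needs N = 142, so 140 is reproduced to within 2 nurses.
- With f = 0.5 as typed, N = 38.
- Within-subject or interaction tests give 14 (f = 0.5) or 44 (f = 0.25). A plain two-sample test at d = 0.5 gives 104 per arm.

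Of the readings tried, d = 0.5 is the one that comes close to 140.

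**2. Variance of the arm contrast**, relative to the outcome variance, one post-baseline score:
- post score alone: 1
- change score: 2(1−ρ) = 2(1−0.5) = 1.00
- baseline-adjusted: 1−ρ² = 1−0.25 = 0.75

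The unadjusted contrasts carry 1.00/0.75 = 1.33 times the variance.

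**3. Power.** Noncentral t with noncentrality d·√(N/4)/√variance, and N−2 degrees of freedom (N−3 with the covariate). At N = 140 the noncentrality is 0.5 × √35 = 2.958 unadjusted and 2.958/√0.75 = 3.416 adjusted.

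| Total N | Change or post score | Baseline-adjusted | Gain (points) |
|---|---|---|---|
| 120 | 77.5% | 88.0% | 10.5 |
| 140 | 83.6% | 92.4% | 8.8 |
| 150 | 86.0% | 94.0% | 8.0 |

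A simulation of 20,000 trials at N = 150 gave 85.9% (post), 86.0% (change) and 93.7% (adjusted).

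**4. Sensitivity.**
- Correlation 0.3, change to adjusted: 63.1% to 81.3% at N = 120 and 72.9% to 89.0% at N = 150. At N = 140: 69.9% change, 83.6% post, 86.8% adjusted.
- Correlation 0.7, change to adjusted: 93.9% to 96.7% at N = 120 and 97.5% to 98.9% at N = 150. At N = 140: 96.7% change, 83.6% post, 98.4% adjusted.
- 150 per arm (N = 300), correlation 0.5: 99.1% to 99.9%.
- Mean of the two follow-up scores, N = 120, correlation 0.5. Change variance is (1+ρ)/2 + 1 − 2ρ = 0.75 and adjusted variance is (1+ρ)/2 − ρ² = 0.50, so power goes from 88.0% to 97.0%.

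**5. Where the extra variance comes from.** If the arms differ by chance at baseline by b SD, the change-score contrast moves by −(1−ρ)b and the post-score contrast by +ρb. At 60 per arm the standard error of b is √(2/60) = 0.18 SD; b = 0.2 moves the two contrasts by −0.10 and +0.10 SD. In variance terms, 2(1−ρ) = (1−ρ²) + (1−ρ)², which at ρ = 0.5 is 1.00 = 0.75 + 0.25. The 0.25 is this imbalance term, already counted in step 2.

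**The case against.** **The loss belongs to a test the plan does not name.** This stands. A reader might infer that the paired t-test itself wastes 8 to 10 points of power and lets baseline imbalance into the arm effect. The protocol does not support that reading: a within-arm test has no between-arm power to lose and no arm effect to distort. The figures describe the two simplest replacements.

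**A reader might also infer bias or false positives from chance imbalance.** That is not supported either. Under randomisation, change-score and post-score contrasts are unbiased and keep the 5% type I error. The imbalance shift is the extra variance in another form and must not be counted as a second harm.

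**Covariates are commonly left to a statistical analysis plan, and none is shown.** The silence about covariates would not be a finding on its own. The protocol goes further, though: its Statistical design commits to a test that cannot answer the two-arm hypotheses. That sentence has to change, and this point concerns what should take its place.

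**The trial appears to have been sized on a repeated-measures between-groups test, which step 3 does not compare.** This is fair, but Statistical design does not name that test. It also averages all three occasions, including baseline, where randomisation makes the expected arm difference zero.

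**The gain is conditional.** This stands. It almost vanishes if 150 means per arm. If 0.5 is Cohen's f (d = 1.0), power exceeds 99.9% either way at N = 120. The Table 1 total favours 75 per arm, and the stated 140 favours d = 0.5.

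**Conclusion.** The point holds in a limited form. The named test gives no arm effect, and the arm comparison that replaces it should use baseline as a covariate. The advantage over change or post scores is about 8 to 10 points of power. That rests on d = 0.5, correlation 0.5, equal arms of 60 to 75 nurses and a single post-baseline score. At correlation 0.3 the gain over change scores is about 16 to 18 points (about 3 over post scores at N = 140). At 0.7 it is about 1 to 3 points over change scores. Adjustment was at least as good as either alternative in every case tried. The loss is one of precision only. The change is worth making because it is nearly free and the sentence must be rewritten anyway.

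**What to change.** In Statistical design, replace the paired t-test as the test of effectiveness. For each outcome, specify an ANCOVA of the post-intervention or three-month score on arm and the nurse's own baseline score on the same scale. Alternatively, specify one mixed model for both follow-ups with arm, time, arm-by-time, baseline and baseline-by-time. Report the adjusted between-arm difference with a 95% CI, and keep the paired before-and-after changes as description only.

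This costs one or two sentences of text and one degree of freedom per covariate. The baseline scores are already collected, so no extra nurses or assessments are needed, and the change also supplies the missing arm comparison.
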